## **PRECIS**

### **Background:**

- Prostate cancer is the most common non-cutaneous malignancy among men in the western world. Prognostic biomarkers would be useful in stratifying patients to different treatments.
- The expression of a testosterone membrane transporter, OATP1B3, is associated with shorter time to progression after hormonal ablation therapy and shorter overall survival in prostate cancer patients. 52% of localized prostate cancer lesions express OATP1B3, while 92% of prostate cancer metastases requiring hormonal ablation treatment, express OATP1B3 in soft tissue lesions. Expression of OATP1B3 also correlates with Gleason grade.
- Current imaging methods cannot predict treatment failure or resistance.
- Gadoxetate disodium (Gd-EOB-DTPA) (Eovist®, Bayer HealthCare Pharmaceuticals Inc. Pittsburgh, PA) is an MR imaging agent which is FDA-approved gadolinium chelate for detecting hepatocellular carcinoma (HCC), as normal hepatocytes express OATP1B3 while most hepatocellular carcinomas do not. However, those HCC's that do take up Eovist® have been shown to express OATP1B3.
- Eovist® may be useful to evaluate OATP1B3 status in patients with prostate cancer and may therefore serve as a prognostic and treatment biomarker.

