In a follow-up study, they further showed that the polymorphism that increases testosterone transport was associated with a shorter time to androgen independence in patients with prostate cancer who are treated with ADT. The study examined the association between this *SLCO1B3* polymorphism and time from ADT to androgen independence, ADT to prostate-specific antigen (PSA) nadir and PSA nadir to androgen independence in 68 Caucasian patients with advanced prostate cancer with metastatic disease (D2) or biochemical failure without metastases (D0) who were treated with ADT. When examined separately, patients with the 334T allele tended to have a shorter time to androgen independence in the D0 ( $P = 0.11$ ) and D2 ( $P = 0.18$ ) groups. Combining these groups and stratifying by stage yielded a statistically significant shorter time to androgen independence in those patients carrying the T allele ( $P = 0.048$ ) [4].

Finally, another study by Wright et al found that CRPC metastases demonstrate increased expression of *SLCO* genes vs. primary CaP. *SLCO1B3* was highly expressed in CRPC metastases vs. untreated CaP (3.6 fold,  $p=0.0517$ ) and *SLCO1B3* SNP rs4149117 (HR 1.76, 95% CI 1.00 - 3.08) had an increased risk of CaP-specific mortality. In their study, CRPC metastases showed increased expression of *SLCO* genes in comparison with primary prostate cancer. Genetic variants of *SLCO1B3* and *SLCO2B1* found to be associated with CaP-specific mortality. Expression and genetic variation of *SLCO* genes which alter androgen uptake was proposed to be important in prostate cancer outcomes and this may allow stratification of patients to more aggressive hormonal therapy or earlier incorporation of non-hormonal based treatment strategies [5].

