## 2 ELIGIBILITY ASSESSMENT AND ENROLLMENT

### 2.1 Eligibility Criteria

#### 2.1.1 Inclusion Criteria

2.1.1.1 Subject is  $\geq 18$  years old.

2.1.1.2 Subjects with clinically localized prostate cancer (outside pathology is acceptable) must have image guided biopsy confirmed prostate cancer and sufficient tissue available (obtained before or after 20 weeks of Eovist® injection) for OATP1B3 expression.

2.1.1.3 Subjects with advanced disease who have failed hormone therapy and who have sufficient tissue (obtained before or after 20 weeks of Eovist® injection) from a soft tissue or metastatic bone lesion (measuring  $\geq 1.5$ cm in diameter at CT or MRI scan) available for OATP1B3 expression.

or

2.1.1.4 Subjects, for whom tissue is not available, must have a soft tissue or metastatic bone lesion that can be biopsied and be willing to undergo percutaneous biopsy to obtain tissue for OATP1B3 expression.

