##### 3.1.1 Eovist® enhanced MRI

MRI will be performed in the Molecular Imaging Clinic. Pre contrast T1, T2 weighted scans with or without endorectal coil will be obtained through the prostate gland, bone metastasis or soft tissue metastasis (usually a lymph node) selected as the target lesion. Then 0.1 ml/kg Eovist® will be administered IV. Scans will be obtained immediately, 10, 20 and 60 minutes after injection using the same settings. Contrast enhancement ratios will be determined at each time point (Section 3.3).

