### **3.5 Correlative Studies**

#### **3.5.1 Imaging Correlation**

A volume of interest (VOI) will be drawn over the target lesion in the baseline and in post-Eovist® injection MR images and the amount of contrast enhancement will be recorded by using dedicated image analysis software (MIM 5.4 Software, MIM Software Inc. Cleveland, OH, USA). Enhancement ratios [(signal enhancement after enhancement-signal enhancement before enhancement)/signal intensity before enhancement] will be calculated on pre and post-injection T1W MR images.

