#### **3.5.3 Histological Correlations**

OATP1B3 expression will be confirmed by staining for OATP1B3 in tissue samples on an investigational basis. IHC analysis will be conducted by one NCI pathologist and will be based on grade of positivity (0 (no staining), 1 (weak staining), 2 (moderate staining) or 3 (strong staining)).

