#### **7.3.2 Secondary Efficacy Analysis**

The secondary objective of the study is to evaluate Eovist® MR parameters with respect to OATP1B3 lesion expression.

Imaging will be performed on 2 subgroups of prostate cancer patients. Subgroup 1 consists of early stage (non-metastatic) patients, subgroup 2 late stage (confirmed metastatic with prior hormonal ablation therapy) patients. It is expected that OATP1B3 expression is higher in late stage patients (subgroup 2) than in early stage patients.

For patients in subgroup 2, expression of OATP1B3 will be determined in soft tissue or bone lesions taken from biopsy and will be correlated with MRI signal change by both Pearson and Spearman correlation coefficient.

As OATP1B3 SNPs also alter androgen uptake, affecting outcome of androgen deprivation therapy (ADT) [3, 4], genotype will also be compared to progression-free survival on ADT. Genotypes will be compared to these endpoints using the chi-squared and/or Fisher's exact test, or the log-rank test as appropriate.

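### Section 7.3.2 correlates OATP1B3 with MRI signal over bone and soft tissue lesions together; a site-adjusted estimate should stand beside the pooled one

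*Combined protocol and SAP*

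**What the plan says.** For the advanced arm, section 7.3.2 says that "expression of OATP1B3 will be determined in soft tissue or bone lesions taken from biopsy and will be correlated with MRI signal change", and that this is done "by both Pearson and Spearman correlation coefficient". Section 3.1.1 allows a "bone metastasis or soft tissue metastasis (usually a lymph node) selected as the target lesion", and sections 2.1.1 and 3.1 likewise accept tissue from either site. No section stratifies or adjusts the correlation by lesion type, limits the mix, or plans results by type.

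The two variables are defined in section 3.5. Staining "will be based on grade of positivity (0 (no staining), 1 (weak staining), 2 (moderate staining) or 3 (strong staining" is an ordinal grade. The enhancement ratio ends in "signal enhancement before enhancement)/signal intensity before enhancement", so each lesion is scaled by its own pre-contrast signal.

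On expression in metastases, the Precis gives one site-labelled figure: "92% of prostate cancer metastases requiring hormonal ablation treatment, express OATP1B3 in soft tissue lesions". Section 1.2.3 adds that SLCO1B3 "was highly expressed in CRPC metastases vs. untreated CaP (3.6 fold"; p = 0.0517), without saying which sites were sampled. Neither gives a figure for bone.

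**The concern.** The correlation in 7.3.2 is the only planned analysis that links Eovist signal to the transporter, and section 1.2.4 makes that link the reason the method might serve as a predictive biomarker. Section 1.2.4 also says that the agent rapidly enhances all vascular structures, so signal change is not specific to OATP1B3. Lesion type could therefore move signal through vascularity or baseline T1 signal. It could also move stain grade, for example through different preparation of bone cores. These mechanisms are assumptions; the documents describe none of them for marrow against lymph node.

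If site lowers both measures in bone, the pooled coefficient turns positive with no association inside either lesion type. If site moves them in opposite directions, a real association is masked. With about 15 patients, the pooled coefficient alone does not show which has happened.

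**Working it through.** **The plan's own figure.** There is none to reproduce. The powers in section 7.4 (83% and more than 95%) belong to the paired pre/post comparison. No power, test level or sample size is stated for the correlation.

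**Inputs from the documents.** Grade 0 to 3 (3.5.3). Advanced arm n = 15 (Precis Design, 7.1), although 3.1 and 7.4 use 10; the two should be reconciled.

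**Inputs assumed.** Bone lesions 3 to 7 of 15; site shifts 0.5 to 2 within-site SD; two-sided 5% test.

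**What n = 15 can show.** Critical |r| = t/√(df + t²).
- Pooled, df = 13, t = 2.160: 2.160/√(13 + 4.667) = 0.51.
- Adjusted for site, df = 12, t = 2.179: 2.179/√(12 + 4.748) = 0.53.
- Separate tests in 7 or 8 patients would need 0.75 or 0.71, so splitting the arm is not useful.

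**Simulation model.** Latent expression X ~ N(0,1) and signal Y = rX + √(1 − r²)·e, with e ~ N(0,1). Bone lesions get X + δx and Y + δy. Grade is the number of cuts (−1, 0, 1) that X exceeds. Pooled: Spearman, tested on 13 df. Adjusted: ranks centred within lesion type, tested on 12 df. With 5,000 trials per setting, simulation error is at most 1.96·√(0.25/5,000) = 1.4 points; repeat runs agree to about two points.

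**(a) No association within site (r = 0), bone lower on both measures.** False-positive rate:

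| Shift on both | Pooled, 3 bone | Pooled, 7 bone | Adjusted |
|---|---|---|---|
| 0.5 SD | about 5% | about 5% | about 5–6% |
| 1 SD | 7% | 11% | about 5–6% |
| 1.5 SD | 13% | 28% | about 5–6% |
| 2 SD | 19% | 54% | about 5–6% |

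With 5 bone lesions the pooled rates at 1, 1.5 and 2 SD are 10%, 22% and 40%. At n = 10 with 4 bone lesions they are 8%, 17% and 32%. If site moves only one measure (1.5 SD), the pooled rate stays at 5%.

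**(b) Same bias without a test.** In a variant with 92% of soft tissue lesions at grade 1 or above and 5 bone lesions, the mean pooled Pearson r is 0.18, 0.33 and 0.47 at 1, 1.5 and 2 SD when the true within-site value is 0.

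**(c) True r = 0.6, 7 bone lesions, opposite shifts.** Power, pooled against adjusted: 41% against 54% at 0.5 SD; 11% against 48% at 1 SD. With no site effect: 58% against 55%.

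**(d) Site acts only through expression (Y = r(X + δx) + √(1 − r²)·e), r = 0.6, 7 bone lesions.** Power, pooled against adjusted: 67% against 55% at 1 SD, 74% against 49% at 1.5 SD, 83% against 44% at 2 SD. Here the difference between sites is genuine signal, and adjustment removes it.

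**The case against.** The strongest reply has four parts.

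- **No test is declared.** Section 7.3.2 names coefficients only, and the 5% level in 7.4 belongs to the pre/post comparison. This stands: the false-positive rates describe a test a reader would naturally apply, not a planned decision. The coefficient itself is still distorted, as (b) shows.
- **The size depends on chosen inputs.** This also stands. With small shifts, few bone lesions or a shift in one measure only, the pooled analysis behaves well. If site shifts enhancement alone, power is lost but no false association arises.
- **The 92% figure proves nothing about site.** Correct. A reader might infer from it that bone expresses less OATP1B3, or that all the evidence on metastases is from soft tissue. The documents support neither: a missing bone figure is not evidence of a difference, and section 1.2.3 reports metastases of unstated site. The figure shows only that the plan has no basis for assuming the two sites alike.
- **Adjustment can hurt.** Result (d) bears this out. A reader might conclude that the within-site correlation should replace the pooled one. That would be wrong if bone lesions enhance less because they truly express less, which is the plan's own hypothesis at work.

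What survives is that the pooled coefficient alone cannot separate these explanations, and the plan provides nothing else.

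**Conclusion.** The gap is real, and its consequence is conditional. The pooled correlation misleads only if site moves both stain grade and enhancement for reasons other than the transporter. Under that assumption the distortion runs from negligible at 0.5 SD to a false-positive rate of 19–54% at 2 SD, and opposite shifts of 1 SD cut power to 11%.

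The documents do not support saying that the pooled correlation is biased, only that it could be and that the plan could not tell. The primary analysis is a within-patient pre/post comparison (7.3.1), so this point does not touch it. The OATP1B3 correlation is exploratory in section 1.1.3, though 7.3.2 calls it secondary, and section 3.7 says that the scan will not direct therapy. The point is therefore of modest severity: a cheap improvement to what the pilot can conclude.

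**What to change.** In section 7.3.2:

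1. Keep the pooled correlation, and add a Spearman correlation adjusted for lesion type (partial, or on ranks centred within type), each with a confidence interval. The signal should be that of the biopsied lesion, so that each patient has one lesion type.
2. Tabulate and plot signal change and stain grade by lesion type.
3. State that a pooled association will be read as transporter-related only if the within-site estimate points the same way.
4. State that the 92% figure refers to soft tissue.

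Lesion type is known once the target is chosen, so no new data are needed. The cost is a few lines of analysis and a less precise adjusted estimate. On the Fisher z scale the approximate 95% half-width goes from 1.96/√12 = 0.57 to 1.96/√11 = 0.59 when site has no effect. The loss is larger when site acts through expression, which is why both estimates should be shown. Separate tests by site are not proposed.

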### **Primary Objective:**

- Evaluate the uptake and retention of Eovist® in prostate cancers.

### **Eligibility:**

- Male subjects  $\geq 18$  years old
- ECOG Performance score of 0 to 2
- Subjects with clinically localized prostate cancer must have image guided biopsy confirmed prostate cancer and sufficient tissue available for OATP1B3 IHC.
- Subjects with advanced disease who have failed hormone therapy and who have sufficient tissue from a soft tissue or metastatic bone lesion (measuring  $\geq 1.5$ cm in diameter at CT or MRI scan) available for OATP1B3 IHC.

or
- Subjects, for whom tissue is not available, must have a soft tissue or metastatic bone lesion that can be biopsied and be willing to undergo percutaneous biopsy to obtain tissue for OATP1B3 expression.

### **Design:**

- This pilot study will accrue 25 subjects divided into two arms: 10 evaluable subjects with localized prostate cancer and 15 evaluable subjects with advanced disease
- Each subject will receive a single IV dose of Eovist® by bolus injection
- All subjects will undergo MRI prior to and immediately after, 10, 20 and 60 minutes post-Eovist® injection

## 1 INTRODUCTION

### 1.1 Study Objectives

#### 1.1.1 Primary Objective

- Evaluate the uptake and retention of Eovist® in prostate cancers

#### 1.1.2 Secondary Objective

- Evaluate MR contrast enhancement parameters following Eovist® injection with respect to Gleason Score and serum PSA levels.

#### 1.1.3 Exploratory Objective

- Evaluate MR contrast enhancement parameters with respect to OATP1B3 expression.

## 1.2 Background and Rationale

### 1.2.1 Study Disease: Prostate Cancer

Prostate cancer is the second most common cause of cancer death in men in the United States. The American Cancer Society estimates that there were 217,730 new cases and 32,050 deaths due to prostate cancer (CaP) in the United States in 2010 [1]. Despite screening with PSA, many patients are diagnosed with advanced stage disease. Androgen deprivation therapy (ADT) is the frontline treatment approach for advanced prostate cancer and may be accomplished by medical or surgical castration. Although the majority of prostate cancer patients initially respond to ADT, disease almost invariably progresses eventually to castration-resistant prostate cancer.

### 1.2.2 Castration Resistant Prostate Cancer (CRPC)

Normal and cancerous growth of the prostate depends on androgen receptor (AR) expression and function. Activation and translocation of the AR by androgens leads to transcriptional activity of AR target genes to induce cell growth and maintain homeostasis. In addition, signaling of growth factors or transport of hormones may have an important role in carcinogenesis and in progression to castrate-resistant disease. Understanding the molecular events that lead to castration resistance is essential in developing successful treatments. Multiple mechanisms involved in the development of CRPC have been proposed, including AR over-expression, AR gene amplification, alteration in AR structure or function, intratumoral androgenic steroid synthesis, ligand-independent AR reactivation by growth factor pathways, as well as AR-independent mechanisms [2]. While many studies have revolved around the AR and its involvement in the androgen signaling axis, relatively little is known about the role of testosterone transport and androgen transporters such as OATP1B3 in prostate cancer. Emerging data suggest a potential role for these steroid transporters in mediating the uptake of androgen into CaP cells and thereby influencing the clinical response to androgen suppression.

### 1.2.3 OATP1B3 Transports Testosterone and affects clinical outcomes in CaP

Previous studies have demonstrated that single nucleotide polymorphisms (SNPs) in *SLCO* genes, which encode OATPs, can markedly alter testosterone transport efficiency. Recently, the [name] lab has specifically evaluated these SNPs and their association with androgen

transport. They showed that a common *SLCO1B3* GG/AA haplotype is associated with impaired testosterone transport and improved survival in patients with prostatic cancer [3]. The study examined (a) the *SLCO1B3* genotype in cancer cells as well as the uptake of testosterone by cells transfected with genetic variants of *SLCO1B3*; (b) the expression of OATP1B3 in normal prostate, benign prostatic hyperplasia, and prostatic cancer; and (c) the role of *SLCO1B3* haplotype on the clinical outcome of Caucasian patients with androgen-independent prostatic cancer. Cells transfected with wild-type (334T/699G) *SLCO1B3*, actively transported testosterone, whereas its uptake was impaired in cells transfected with a gene carrying both 334G and 699A single nucleotide polymorphisms. Approximately half of localized prostatic cancers over-express OATP1B3 compared with normal or benign hyperplastic tissue; patients with *SLCO1B3* 334GG/699AA haplotype showed longer median survival (8.5 versus 6.4 years;  $P = 0.020$ ) and improved survival probability at 10 years (42% versus 23%;  $P < 0.023$ ) than patients carrying TT/AA and TG/GA haplotypes. The common *SLCO1B3* GG/AA haplotype is associated with impaired testosterone transport and improved survival in patients with prostatic cancer [3].

In a follow-up study, they further showed that the polymorphism that increases testosterone transport was associated with a shorter time to androgen independence in patients with prostate cancer who are treated with ADT. The study examined the association between this *SLCO1B3* polymorphism and time from ADT to androgen independence, ADT to prostate-specific antigen (PSA) nadir and PSA nadir to androgen independence in 68 Caucasian patients with advanced prostate cancer with metastatic disease (D2) or biochemical failure without metastases (D0) who were treated with ADT. When examined separately, patients with the 334T allele tended to have a shorter time to androgen independence in the D0 ( $P = 0.11$ ) and D2 ( $P = 0.18$ ) groups. Combining these groups and stratifying by stage yielded a statistically significant shorter time to androgen independence in those patients carrying the T allele ( $P = 0.048$ ) [4].

Finally, another study by Wright et al found that CRPC metastases demonstrate increased expression of *SLCO* genes vs. primary CaP. *SLCO1B3* was highly expressed in CRPC metastases vs. untreated CaP (3.6 fold,  $p=0.0517$ ) and *SLCO1B3* SNP rs4149117 (HR 1.76, 95% CI 1.00 - 3.08) had an increased risk of CaP-specific mortality. In their study, CRPC metastases showed increased expression of *SLCO* genes in comparison with primary prostate cancer. Genetic variants of *SLCO1B3* and *SLCO2B1* found to be associated with CaP-specific mortality. Expression and genetic variation of *SLCO* genes which alter androgen uptake was proposed to be important in prostate cancer outcomes and this may allow stratification of patients to more aggressive hormonal therapy or earlier incorporation of non-hormonal based treatment strategies [5].

#### 1.2.4 Rationale

No currently used imaging method evaluates the status of the OATP1B3 transporter. Such a method might be important in stratifying risk factors in patients, both with localized and with metastatic disease.

Eovist® (gadoxetate disodium) is a gadolinium-based contrast agent which was approved by the FDA in 2008 [6]. It is indicated for intravenous use in T1-weighted magnetic resonance imaging (MRI) of the liver to detect and characterize lesions in adults with known or suspected focal liver disease, particularly in the diagnosis of hepatocellular carcinoma (HCC). The agent

is taken up by normal hepatocytes and lesions that contain normal hepatocytes (e.g. focal nodular hyperplasia). The majority of HCCs do not take up Eovist® and so the agent has become useful in the workup of suspected HCC. However, some HCC tumors do take up Eovist® and this uptake has been correlated with their OATP1B3 expression [7, 8].

The agent is injected intravenously. Because it is a low molecular weight imaging agent it rapidly enhances all vascular organs and structures. However, it was not retained by non OATP1B3 expressing tissue and so at 20 minutes a correlation was made between OATP1B3 expressing lesions (persistent enhancement) and non OATP1B3 expressing lesions (washout of enhancement).

Thus, Eovist® will be used in patients with localized and metastatic prostate cancer in order to determine if this method is feasible to observe differences in uptake times in prostate cancers and whether these differences correlate with OATP1B3 expression in prostate cancer and therefore, might serve as a predictive biomarker.

## 2 ELIGIBILITY ASSESSMENT AND ENROLLMENT

### 2.1 Eligibility Criteria

#### 2.1.1 Inclusion Criteria

2.1.1.1 Subject is  $\geq 18$  years old.

2.1.1.2 Subjects with clinically localized prostate cancer (outside pathology is acceptable) must have image guided biopsy confirmed prostate cancer and sufficient tissue available (obtained before or after 20 weeks of Eovist® injection) for OATP1B3 expression.

2.1.1.3 Subjects with advanced disease who have failed hormone therapy and who have sufficient tissue (obtained before or after 20 weeks of Eovist® injection) from a soft tissue or metastatic bone lesion (measuring  $\geq 1.5$ cm in diameter at CT or MRI scan) available for OATP1B3 expression.

or

2.1.1.4 Subjects, for whom tissue is not available, must have a soft tissue or metastatic bone lesion that can be biopsied and be willing to undergo percutaneous biopsy to obtain tissue for OATP1B3 expression.

